# 5. STATISTICAL ANALYSES

## 5.1 GENERAL CONSIDERATION

The analyses outlined in this statistical analysis plan (SAP) supersede those specified in the protocol for the purpose of a regulatory filing.

ORR, duration of response (DOR), and PFS are determined by the investigator and by BICR according to RECIST v1.1 and RANO respectively. Secondary endpoint analyses for the endpoint by BICR are as well sensitivity analyses for that endpoint by investigator.

CNS ORR and DOR are determined in patients with CNS metastases at baseline only by BICR according to RECIST v1.1.

The analyses will be performed in the populations specified in Section 4.

# 5.2 PARTICIPANT DISPOSITION

The patient status (on treatment, off treatment, in long-term follow-up, lost-to-follow-up and dead) and the time of efficacy follow-up will be summarized.

## 5.3 PRIMARY ENDPOINT ANALYSIS

## 5.3.1 Definition of Primary Endpoint

The primary efficacy endpoint is confirmed ORR as determined by the investigator in patients with ALK fusion solid tumors (excluding enrolled patients with CUP and CNS primary tumors). An objective response is defined as a CR or a PR according to RECIST v1.1. Confirmation of objective response is required (confirmed ≥ 28 days apart in two separate tumor assessments). Patients not meeting this criterion (including patients without a post-baseline tumor assessment) will be considered as non-responders. ORR is defined as the proportion of patients with measurable disease at baseline who have an objective response in the response-evaluable population.

# 5.3.2 Main Analytical Approach for Primary Endpoint

An estimate of the confirmed ORR and its two-sided 95% CI using the Clopper-Pearson method will be calculated. The confirmed ORR will be tested against the minimal clinically relevant ORR of 30% in this tissue-agnostic, biomarker-defined population with no available treatment options at the 5% two-sided significance level, i.e., the lower limit of the Clopper-Pearson CI must be bigger than 30%.

## 5.3.3 Sensitivity Analyses for Primary Endpoint

see Section 5.1.

# 5.3.4 Supplementary Analyses for Primary Endpoint

# 5.3.4.1 Subgroup Analyses for Primary Endpoint

The generalizability of the confirmed ORR results will be investigated by estimating the effect in subgroups including by sex, age, and race.

## 5.4 SECONDARY ENDPOINTS ANALYSES

## 5.4.1 Key Secondary Endpoint

The key secondary efficacy endpoint is confirmed ORR as determined by the BICR in patients with ALK fusion solid tumors (excluding enrolled patients with CUP and CNS primary tumors). The same analyses as for the primary endpoint will be applied.

## 5.4.2 Supportive Secondary Endpoints

## 5.4.2.1 Duration of Response

DOR is defined as the time from the date of the first occurrence of a CR or a PR (whichever status is recorded first) to the date of the first documented disease progression or death due to any causes, whichever occurred first. The DOR will be assessed in patients who had a confirmed objective response during the study, as determined by the investigator or BICR per RECIST v1.1. Patients who have not progressed or died at the time of analysis will be censored at the last tumor assessment date. If no tumor assessments are performed after the date of the first occurrence of a CR or a PR, DOR will be censored at the date of the first occurrence of a CR or a PR. The Kaplan-Meier methodology will be used to estimate the median DOR and to construct survival curves. The Brookmeyer-Crowley methodology will be used to construct the 95% CI for the median DOR (Brookmeyer and Crowley 1982).

# 5.4.2.2 Progression-Free Survival

Progression free survival is defined as the time from the first date of treatment to the date of first documented disease progression or death, whichever occurs first. Disease progression will be assessed by the investigator or the BICR using RECIST v1.1. Patients who have not experienced disease progression or died at the time of analysis will be censored at the last tumor assessment date. Patients with no post-baseline tumor assessment will be censored at the first date of treatment. The analysis methods are the same as for the DOR defined above.

# 5.4.2.3 Overall Survival

Overall survival is defined as the time from the first date of treatment to the date of death due to any cause. Patients who are not reported as dead at the time of the analysis will be censored at the date when they were last known to be alive. If no post-baseline information is available, then OS will be censored at the date of the first treatment. The analysis methods are the same as for the DOR defined above.

# 5.4.2.4 CNS Objective Response Rate

For patients with ALK-fusion positive tumors (excluding patients with CUP and patients with CNS primary tumors), who present with measurable CNS metastases at baseline

an analysis of CNS ORR defined as the percentage of patients who achieve a best overall response of a CR or a PR of CNS lesion (defined according to RECIST v1.1) will also be performed in the response-evaluable population with measurable CNS disease at baseline. CNS CR and PR will be assessed by BICR. The analysis methods are the same as for the primary endpoint. Confirmation of objective response is not required.

# 5.4.2.5 CNS Duration of Response

For patients who had a CNS objective response during the study, an analysis of CNS DOR, defined as the time from the date of the first occurrence of CNS CR or PR (whichever status is recorded first) to the date of the first documented disease CNS progression or death due to any causes, whichever occurred first, will be conducted. CNS disease progression will be assessed by BICR using RECIST v1.1. The analysis methods are the same as for the DOR defined above. Confirmation of objective response is not required.

# 5.4.2.6 Efficacy in Patients with Primary CNS Tumors

For patients with primary CNS tumors with measurable disease at baseline who have a baseline tumor assessment per the investigator according to RANO criteria and receive at least one dose of alectinib:

- ORR, DOR, and PFS in all ALK fusion-positive patients who have measurable disease at baseline as determined by both the investigator and BICR
- OS

The analysis methods are the same as for the respective endpoints defined above.

#### 5.4.2.7 Efficacy in Patients with Solid Tumors without ALK Fusions, Harboring Defined ALK Mutations (R1275Q, F1245C, F1174X, with X being any other amino acid)

For patients with solid tumors without ALK fusions, harboring defined ALK mutations (R1275Q, F1245C, F1174X, with X being any other amino acid) and receive at least one dose of alectinib:

- ORR, DOR, and PFS as determined by the investigator and by BICR according to RECIST v1.1
- CNS ORR and DOR in patients with CNS metastases at baseline by BICR according to RECIST v1.1
- OS

Confirmation of objective response is not required.

The analysis methods are the same as for the respective endpoints defined above.

## 5.4.2.8 Efficacy in Patients with CUP

For patients with CUP who receive at least one dose of alectinib:

- ORR, DOR, and PFS as determined by both the investigator and BICR according to RECIST v1.1
- CNS ORR and DOR in patients with CNS metastases at baseline, as determined by BICR according to RECIST v1.1
- OS

The analysis method is the same as for the respective endpoints defined above.

For some populations, depending on the number of patients, a formal analysis will not be produced; instead, listings or spider plots could be used.

## 5.5 EXPLORATORY ENDPOINTS ANALYSES

#### 5.5.1.1 Efficacy in Patients with ALK-Positive CUP and Non-CUP Solid Tumors

For patients with ALK-positive CUP and non-CUP solid tumors who receive at least one dose of alectinib:

- ORR, DOR, and PFS as determined by both the investigator and BICR according to RECIST v1.1
- CNS ORR and DOR in patients with CNS metastases at baseline, as determined by BICR according to RECIST v1.1
- OS

The analysis methods are the same as for the respective endpoints defined above.

## 5.5.1.2 Patient Reported Outcomes: EORTC Data

The quality of life questionnaire core 30 (QLQ-C30) questionnaires will be used to assess the impact of alectinib on patients' quality of life and daily function. All patients who receive at least one dose of alectinib will be analyzed. Completion rates will be summarized by number and proportion of patients among those expected to complete each questionnaire at each timepoint. Reasons for non-completion will be summarized at each timepoint if available.

The European Organization for Research and Treatment of Cancer (EORTC) QLQ-C30 (Version 3) data will be scored according to the EORTC scoring manual (Fayers et al. 2001). In the event of incomplete data, if the scale has more than 50% of the constituent items completed, a pro-rated score will be computed consistent with the scoring manual and validation papers of the measure. For subscales with less than 50% of the items completed, the subscale will be considered missing.

Summary statistics (mean, standard deviation, median, and range) of linearly transformed absolute scores and mean changes from baseline will be calculated for the function, disease/treatment-related symptom-, and Global Health Status (GHS)/Quality

of life (QoL) scales of the EORTC QLQ-C30 at each assessment timepoint. The mean (and 95% CI) and median of the absolute scores and the changes from baseline will be reported on patients with a baseline and at least one post-baseline assessment. Previously published minimally important differences will be used to identify meaningful change from baseline within the treatment group on the functional and GHS/QoL scales (Osoba et al. 1998; Cocks et al. 2011).

#### 5.6 SAFETY ANALYSES

Safety analyses will be performed on the safety evaluable population, defined as all enrolled patients who received any amount of study drug

#### 5.6.1 Extent of Exposure

Study drug exposure, including treatment duration, number of doses, dose intensity and total cumulative dose will be summarized with descriptive statistics.

## 5.6.2 Adverse Events

Verbatim description of adverse events (AEs) will be mapped to Medical Dictionary for Regulatory Activities thesaurus terms and graded according to National Cancer Institute Common Terminology Criteria for Adverse Events (NCI CTCAE) v5.0.

After informed consent has been obtained but prior to initiation of study drug, only serious AEs caused by a protocol-mandated intervention (e.g., invasive procedures such as biopsies, discontinuation of medications) are collected.

After initiation of study drug, all adverse events will be collected until 28 days after the final dose of study drug.

After the end of the adverse event reporting period, all deaths, regardless of cause, and serious adverse events that are believed to be related to prior exposure to study drug are collected.

All AEs that occur on or after the first study drug dose (treatment-emergent AEs) will be reported. They will be summarized using descriptive statistics (i.e., frequencies and percentages) by Medical Dictionary for Regulatory Activities (MedDRA) term, appropriate MedDRA levels, and NCI CTCAE v5.0 grade, regardless of relationship to study drug as assessed by the investigator. For each patient, if multiple incidences of the same adverse events occur, the maximum severity reported will be used in the summaries.

The following treatment-emergent adverse events will be summarized separately:

- AEs
- AEs leading to withdrawal of study drug
- AEs leading to dose reduction or interruption

Alectinib—F. Hoffmann-La Roche Ltd **Statistical Analysis Plan** BO41929

- Grade 3/4 AEs, Grade 5 AEs, serious adverse events
- AEs of special interest

All deaths and causes of death will be summarized.

Subgroup analyses will be performed to evaluate the safety profile within subgroups of patients, including by sex, age (< 65 years vs.  $\geq$  65 years), region, and race.

## 5.6.3 Laboratory Data

Clinically relevant shifts from baseline in NCI CTCAE v5.0 grade (defined as shifts from Grade 0, 1, or 2 at baseline to Grade 3 or 4 post baseline) will be also provided. Of note, abnormal laboratory data that are clinically significant will be reported as AEs and summarized in the AE tables.

A Hy's Law analysis will be provided: the finding of an elevated ALT or AST  $(>3 \cdot baseline value)$  in combination with either an elevated total bilirubin  $(>2 \cdot upper limit of normal)$  or clinical jaundice in the absence of cholestasis or other causes of hyperbilirubinemia is considered to be an indicator of severe liver injury (as defined by Hy's Law).

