4.1.1 Inclusion Criteria

Patients must meet the following criteria for study entry:

- Signed Informed Consent Form
- Age ≥ 18 years at time of signing Informed Consent Form
- Histologically confirmed locally advanced or metastatic solid tumor excluding lung cancer
- ALK-positive tumor per FMI NGS (NGS F1CDx, F1LCDx, or F1HEME) or per local accredited laboratory using validated NGS testing of tumor tissue or peripheral blood:
 - ALK fusion
 - The following ALK-activating mutations: R1275Q, F1245C, or F1174X
 - Local ALK test report (only for cases with local ALK testing; see Section 4.6.5.3)
- Disease progression on prior treatment, or previously untreated disease with no available acceptable treatment
- Other prior cancer therapies are allowed, including investigational drugs, if any treatment-related toxicities (excluding alopecia) have resolved to Grade 1 or better and laboratory values as defined in inclusion criteria, and meet the following washout criteria prior to first dose of alectinib:
 - At least 4 weeks must have elapsed since the last dose of the prior cytotoxic chemotherapy or antibody-directed therapy.
 - At least 7 days must have elapsed since prior tyrosine kinase inhibitor (TKI) therapy.
 - At least 14 days must have elapsed since prior radiotherapy.
- Measurable disease at baseline, as assessed by investigator (by RECIST v1.1, or according to RANO criteria for patients with primary CNS tumors)
 - For primary CNS tumors, only MRI scans will be accepted. If the local radiology facility cannot perform MRI, the patient will be excluded from the study.
- Life expectancy of at least 12 weeks in the opinion of the investigator
- Eastern Cooperative Oncology Group (ECOG) Performance Status of 0–2 (see Appendix 3)
- Adequate hematologic function:
 - Platelet count \geq 100 \times 10⁹/L
 - Absolute neutrophil count \geq 1500/µL
 - Hemoglobin \geq 9 g/dL
- Adequate hepatic function:
 - ALT (SGPT) and AST (SGOT) $\leq 2.5 \times$ upper limit of normal (ULN) ($\leq 5 \times$ ULN for patients with concurrent liver metastasis)
 - Bilirubin ≤2 mg/dL

Alectinib—F. Hoffmann-La Roche Ltd 42/Protocol BO41929, Version 4

- Adequate renal function:
 - Serum creatinine $< 2 \times ULN$
 - Calculated creatinine clearance of ≥ 60 mL/min (Cockcroft-Gault formula)
- Patients with primary CNS tumors are eligible
- Patients with CUP tumors are eligible

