Hepatotoxicity	Liver test laboratory abnormalities are to be reported as AEs only if fulfilling the criteria listed in Section 5.3.5.4 and Section 5.3.5.6. At any time during the study treatment, if symptoms compatible with liver injury are observed, liver enzymes should be measured as soon as possible.	

Event	Action to Be Taken	
Hepatotoxicity (cont.)	Regardless of relatedness to alectinib , the grade-dependent rules for dose interruptions and dose modification outlined in the first section of this table must be followed.	
	In addition, study drug treatment has to be permanently discontinued if any of the following occurs:	
	• First observation of ALT or AST >8 × ULN	
	 ALT or AST >5× ULN for more than 2 weeks 	
	 First observation of ALT or AST >3× ULN and total bilirubin >2×ULN 	
	 First observation of ALT or AST >3× ULN and the appearance of jaundice or signs of hepatic dysfunction or other symptoms (such as fatigue, nausea, vomiting, right upper quadrant pain or tenderness, fever, rash, or eosinophilia [>5%]) 	
	 Following study drug discontinuation, weekly monitoring of laboratory values should continue until the abnormal values have normalized to pretreatment levels and/or an adequate explanation of the abnormal value is found 	
	 Resumption of study drug is not allowed in patients discontinuing because of any of the above criteria 	
Gastrointestinal tract AEs (e.g., nausea, vomiting, diarrhea, stomatitis)	The events are expected to be minimized by taking the study drug with a meal. If GI events occur, appropriate measures should be taken in accordance with local clinical practice guidelines.	
	In case of AEs related to alectinib, follow the grade-dependent rules for dose interruption and modification outlined in the first section of this table.	
Skin disorder AEs (e.g., phototoxicity, rash)	 Patients should be advised to avoid prolonged sun exposure while taking alectinib and for at least 7 days after study drug discontinuation. Patients should also be advised to use a broad-spectrum sunscreen and lip balm of at least SPF 50 to help protect against potential sunburn during this period. In case of AEs related to alectinib, follow the grade-dependent rules for dose interruption and modification outlined in the first section of this table. 	

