- Results in persistent or significant disability/incapacity (i.e., the adverse event results in substantial disruption of the patient's ability to conduct normal life functions)
- Is a congenital anomaly/birth defect in a neonate/infant born to a mother exposed to study drug

Alectinib—F. Hoffmann-La Roche Ltd

 Is a significant medical event in the investigator's judgment (e.g., may jeopardize the patient or may require medical/surgical intervention to prevent one of the outcomes listed above)

The terms "severe" and "serious" are not synonymous. Severity refers to the intensity of an adverse event (e.g., rated as mild, moderate, or severe, or according to NCI CTCAE; see Section 5.3.3); the event itself may be of relatively minor medical significance (such as severe headache without any further findings).

Severity and seriousness need to be independently assessed for each adverse event recorded on the eCRF.

Serious adverse events are required to be reported by the investigator to the Sponsor immediately (i.e., no more than 24 hours after learning of the event; see Section 5.4.2 for reporting instructions).

5.2.3 Adverse Events of Special Interest (Immediately Reportable to the Sponsor)

Adverse events of special interest are required to be reported by the investigator to the Sponsor immediately (i.e., no more than 24 hours after learning of the event; see Section 5.4.2 for reporting instructions). Adverse events of special interest for this study are as follows:

- Cases of potential drug-induced liver injury that include an elevated ALT or AST in combination with either an elevated bilirubin or clinical jaundice, as defined by Hy's Law (see Section 5.3.5.6)
- Suspected transmission of an infectious agent by the study drug, as defined below

Any organism, virus, or infectious particle (e.g., prion protein transmitting transmissible spongiform encephalopathy), pathogenic or non-pathogenic, is considered an infectious agent. A transmission of an infectious agent may be suspected from clinical symptoms or laboratory findings that indicate an infection in a patient exposed to a medicinal product. This term applies only when a contamination of the study drug is suspected.

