5.3.5.4 Abnormal Laboratory Values

Not every laboratory abnormality qualifies as an adverse event. A laboratory test result must be reported as an adverse event if it meets any of the following criteria:

- Is accompanied by clinical symptoms
- Results in a change in study treatment (e.g., dosage modification, treatment interruption, or treatment discontinuation)
- Results in a medical intervention (e.g., potassium supplementation for hypokalemia) or a change in concomitant therapy
- Is clinically significant in the investigator's judgment

Note: For oncology trials, certain abnormal values may not qualify as adverse events.

It is the investigator's responsibility to review all laboratory findings. Medical and scientific judgment should be exercised in deciding whether an isolated laboratory abnormality should be classified as an adverse event.

Alectinib—F. Hoffmann-La Roche Ltd 83/Protocol BO41929, Version 4

If a clinically significant laboratory abnormality is a sign of a disease or syndrome (e.g., alkaline phosphatase and bilirubin $5 \times ULN$ associated with cholestasis), only the diagnosis (i.e., cholestasis) should be recorded on the Adverse Event eCRF.

If a clinically significant laboratory abnormality is not a sign of a disease or syndrome, the abnormality itself should be recorded on the Adverse Event eCRF, along with a descriptor indicating whether the test result is above or below the normal range (e.g., "elevated potassium," as opposed to "abnormal potassium"). If the laboratory abnormality can be characterized by a precise clinical term per standard definitions, the clinical term should be recorded as the adverse event. For example, an elevated serum potassium level of 7.0 mEq/L should be recorded as "hyperkalemia."

Observations of the same clinically significant laboratory abnormality from visit to visit should only be recorded once on the Adverse Event eCRF (see Section 5.3.5.3 for details on recording persistent adverse events).

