5.3.5.6 Abnormal Liver Function Tests

The finding of an elevated ALT or AST (> $3 \times$ ULN) in combination with either an elevated total bilirubin (> $2 \times$ ULN) or clinical jaundice in the absence of cholestasis or other causes of hyperbilirubinemia is considered to be an indicator of severe liver injury (as defined by Hy's Law). Therefore, investigators must report as an adverse event

(adverse event of special interest or serious adverse event) the occurrence of either of the following:

- Treatment-emergent ALT or AST $> 3 \times ULN$ in combination with total bilirubin $> 2 \times ULN$
- Treatment-emergent ALT or AST $> 3 \times$ ULN in combination with clinical jaundice

The most appropriate diagnosis or (if a diagnosis cannot be established) the abnormal laboratory values should be recorded on the Adverse Event eCRF (see Section 5.3.5.4) and reported to the Sponsor immediately (i.e., no more than 24 hours after learning of the event), either as a serious adverse event or an adverse event of special interest (see Section 5.4.2).

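### The SAP's Hy's Law analysis sets the ALT/AST criterion at more than 3 times baseline, while the protocol sets it at more than 3 times ULN, so cases can be missed or over-counted depending on the baseline value

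*SAP*

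**What the plan says.** Protocol Section 5.3.5.6 defines the Hy's Law finding on the ULN scale: "The finding of an elevated ALT or AST (> $3 \times$ ULN") together with total bilirubin above 2 x ULN or clinical jaundice, when cholestasis and other causes of raised bilirubin are absent. It then lists two reportable events on the same scale. One pairs the enzyme rise with bilirubin above 2 x ULN. The other reads "Treatment-emergent ALT or AST $> 3 \times$ ULN in combination with clinical jaundice".

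The rest of the protocol is consistent with this. The adverse event of special interest in Section 5.2.3 ("Cases of potential drug-induced liver injury that include an elevated ALT or AST in combination with either an elevated bilirubin or clinical jaundice") takes its threshold by cross-reference to Section 5.3.5.6. The hepatotoxicity row of Table 1 in Section 5.1.2.3 includes "First observation of ALT or AST >3× ULN and total bilirubin >2×ULN".

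SAP Section 5.6.3 plans a Hy's Law analysis and gives nearly the same definition, including the exclusion for cholestasis and other causes. It differs in one term: ALT or AST must exceed three times the "baseline value)$ in combination with either an elevated total bilirubin" above twice ULN, or jaundice. Bilirubin stays on the ULN scale. No reason is given, and no second, ULN-based version is planned.

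**The concern.** The SAP calls its criterion Hy's Law, but it is not the criterion the protocol uses under that name. Eligibility permits raised liver enzymes at entry: ALT and AST up to 2.5 x ULN, or up to 5 x "ULN for patients with concurrent liver metastasis". A multiple of baseline therefore gives a higher cut-off than the protocol's in patients who start above ULN, and a lower one in those who start below it.

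Protocol Section 6.5 contains no Hy's Law analysis to fall back on. SAP Section 5.1 states: "The analyses outlined in this statistical analysis plan (SAP) supersede those specified in the protocol for the purpose of a regulatory filing". SAP Section 5.6.3 is therefore the text an analyst would program from. It is also the only planned analysis that applies joint enzyme and bilirubin criteria to the laboratory data, so it should be able to cross-check the cases investigators report. With a different cut-off, a disagreement between the two sources could not be interpreted.

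**Working it through.** The plan states no figure to reproduce. The check compares two thresholds.

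**Inputs**
- SAP criterion: ALT or AST > 3 x baseline (SAP 5.6.3).
- Protocol criterion: ALT or AST > 3 x ULN, treatment-emergent for reporting (Protocol 5.3.5.6).
- Baseline: the last value before first dose (SAP 5.7.2).
- Allowed baseline at entry: up to 2.5 x ULN, or up to 5 x ULN with liver metastasis (Protocol 4.1.1).

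**Formula.** Write baseline as b and the on-treatment peak as p, both in multiples of ULN. The SAP flags p > 3b and the protocol flags p > 3. The rules agree for every p only if 3b = 3, that is b = 1.
- For b > 1, protocol cases with 3 < p ≤ 3b are missed by the SAP.
- For b < 1, patients with 3b < p ≤ 3 are SAP cases but not protocol cases.

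All rows below assume that bilirubin is above 2 x ULN or jaundice is present, and that the cholestasis/other-cause exclusion does not apply.

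| Baseline b (x ULN) | SAP cut-off 3b (x ULN) | Peak values where the rules differ (x ULN) |
|---|---|---|
| 0.5 | 1.5 | above 1.5, up to 3: over-counted |
| 0.8 | 2.4 | above 2.4, up to 3: over-counted |
| 1.0 | 3.0 | none |
| 1.5 | 4.5 | above 3, up to 4.5: missed |
| 2.0 | 6.0 | above 3, up to 6: missed |
| 2.5 (entry limit without liver metastasis) | 7.5 | above 3, up to 7.5: missed |
| 3.0 (liver metastasis only) | 9.0 | above 3, up to 9: missed |

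The baselines below ULN are illustrative.

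**Worked example.** A patient starts at 2.4 x ULN and peaks at 7 x ULN. The ratio to baseline is 7 / 2.4 = 2.92, which is below 3, so the SAP does not flag the patient. The peak of 7 exceeds 3 and the baseline of 2.4 does not, so this is a treatment-emergent protocol case.

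**Baselines above 3 x ULN.** These can occur only with liver metastasis. The patient already exceeds the protocol cut-off before treatment, so reportability depends on treatment-emergent, which the protocol does not define numerically. No missed range is claimed here.

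**After the change.** With ALT/AST > 3 x ULN in the SAP, the cut-off is 3 at every baseline and both ranges vanish.

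**The case against.** The strongest counter-argument is that little is lost. Every missed case is, by construction, one the investigator must report as a serious adverse event or an adverse event of special interest, and SAP Section 5.6.2 summarises both. Table 1 also lists ALT or AST above 3 x ULN with bilirubin above 2 x ULN, or with jaundice, among its discontinuation criteria. Under Protocol Section 5.3.5.4, a laboratory result must be reported as an adverse event if it "Results in a change in study treatment (e.g., dosage modification, treatment interruption, or treatment discontinuation"), so the case should also appear among adverse events leading to withdrawal. This stands, and it is why the point is minor. Those summaries do, however, depend on investigator reporting, which the laboratory analysis ought to check independently.

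A second argument is that no miscount is shown. The documents give no ALT/AST distribution, and the bilirubin or jaundice condition must also be met in patients whose entry bilirubin was at most 2 mg/dL. This also stands: the mismatch is certain, but its yield in patients is not.

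Third, Protocol Section 5.3.5.6 is not uniform. Its definition sentence carries the cholestasis/other-cause exclusion but not treatment-emergent, and its reportable-event bullets carry treatment-emergent but not the exclusion. The limit of 3 x ULN on the missed range rests on the bullets. Under the definition sentence alone, misses would extend to baselines of 5 x ULN, so the limit used here is conservative. The uneven exclusion is a separate reason why the SAP output and the reported cases could differ.

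Finally, the SAP may have intended to allow for abnormal baselines. Nothing in it says so, and the rule applies to every patient, including those with normal baselines, for whom it lowers the cut-off.

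**Conclusion.** The point holds and is minor. Programmed as written, SAP Section 5.6.3 would classify patients differently from the trial's own Hy's Law definition at every baseline below ULN and at baselines above 1 and up to 3 x ULN. At the entry limit without liver metastasis, the SAP cut-off is 7.5 x ULN against the protocol's 3 x ULN.

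This rests on the SAP sentence being used as the derivation, on the bilirubin or jaundice condition being met, and on the cholestasis/other-cause exclusion not applying. With about 50 ALK-fusion patients and an unstated number of others, few are likely to be affected; the number cannot be computed. The effect is confined to one descriptive safety output. The primary endpoint, adverse event reporting and patient management are unaffected.

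**What to change.** In SAP Section 5.6.3, replace the ALT/AST criterion with treatment-emergent ALT or AST above 3 x ULN, to match Protocol Section 5.3.5.6. Add a sentence saying how treatment-emergent is derived, for example baseline at or below 3 x ULN with any post-dose value above 3 x ULN. List patients with baseline above 3 x ULN individually. If a baseline-multiple view is wanted, keep it as a labelled supplementary display.

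This change does not remove the difference over the cholestasis/other-cause exclusion, so the output should state whether that exclusion has been applied.

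The cost is one term and one derivation sentence, plus a short listing. ALT, AST and bilirubin are already collected, and the SAP's bilirubin criterion and the eligibility limits already need the ULN. No clinical rule changes.
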